## Background

Cervical myelopathy is commonly associated with degenerative spinal disease. It is a common cause of spinal cord dysfunction in the aging population. The predominant pathology seen in these patients is spondylosis which includes degeneration of joints, discs and ligaments. (1). Spinal cord ischemia may also contribute to these pathological processes but the exact mechanism remains unclear. Magnetic resonance imaging may reveal disc herniation, osteophytic narrowing of the spinal canal and hypertrophic changes to the ligamentum flavum (2). Patients may present with a wide range of symptoms ranging from neck pain and decreases in dexterity in mild cases to sphincter dysfunction and complete loss of motor function in severe cases (3). Dysfunction of the autonomic nervous system is also evident in many cases of cervical myelopathy (4). In many of these patients, the spinal cord is at risk of ischemia due to decreased blood flow as a result of compressive lesions. Any further reduction in spinal cord blood flow may not be well tolerated. Mean arterial pressure (MAP) is one of the important factors that determine the adequacy of perfusion to the spinal cord and hypotension has been shown to be associated with poor outcome in patients with spinal cord injury.

Autonomic nervous system dysfunction is often seen in patients with acute spinal cord injury. (5). A recent study has shown autonomic nervous system involvement in up to 50% of patients with compressive cervical myelopathy (4). The autonomic nervous system (ANS) is responsible for the normal regulation of visceral organ function including the cardiovascular system. They are the primary regulator of heart rate and blood pressure.

Surgical treatment of cervical myelopathy may involve anterior and/or posterior decompression of spinal cord with or without instrumented fusion. The main purpose of the surgery is to prevent further deterioration of spinal cord function. Patients with cervical myelopathy often pose a significant challenge to the anesthesiologists. In addition to challenges with airway management and patient positioning, the most important anesthetic consideration in these patients is to maintain the mean arterial blood pressure (MAP) >70 mmHg during the surgery.

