### HRV as a predictor of Hypotension under Anesthesia

Haemodynamic stability under anaesthesia depends in a large part on the integrity of the autonomic pathways that feedback into cardiovascular regulatory centres and control variables like heart rate, contractility and vascular tone. As an indicator of autonomic function, heart rate variability may therefore have a role to play in predicting haemodynamic instability. Studies show that heart rate variability may be used as a predictor of haemodynamic fluctuations under anaesthesia. Hanss et al (12) have shown that the LF: HF ratio can be used to predict severe hypotension during spinal anaesthesia. In a study of patients under general anaesthesia Huang et al (13) showed that spectral analysis of heart rate variability could be used as a sensitive predictor of hypotension and that heart rate variability may be superior to traditional tests of autonomic function.

Heart rate variability is being increasingly used in the setting of general and regional anaesthesia as both a diagnostic and prognostic tool (8).

At present the incidence of decreased HRV in patients with cervical myelopathy is unknown as well as whether this is predictive of hypotension on induction of general anaesthesia. Therefore, the aim of our study is to determine the incidence of abnormalities in HRV in patients undergoing surgery for cervical myelopathy and to determine whether decreased heart rate variability is predictive of hypotension on induction in these patients.

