## Proposed methodology

### Study design

This is a single centre, prospective observational study.

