## Analysis

The incidence of low HRV as indicated by a total power below the normal range of  $3466 \text{ ms}^2 \pm 1018 \text{ ms}^2$  will be determined as well as the incidence of hypotension. We will determine the correlation between low HRV, hypotension and the severity of myelopathy as determined by the Japanese Orthopaedic Association score. Non-parametric HRV within group data will be analysed with the Wilcoxon matched pairs test. Comparisons of non-parametric HRV data between groups will be performed using the Mann–Whitney test. Student t test will be used for parametric data.

Definitions:

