### *1. Heart rate variability*

The Task Force of the European Society of Cardiology and the North American Society of Pacing and Electrophysiology has standardized guidelines for the measurement of heart rate variability (14). These recordings will be analysed and power spectrum densities will be calculated for total power (TP) which is a measure of heart rate variability. Low frequencies (LF), high frequencies (HF) and LF: HF ratio will also be analysed. Based on HRV values, two groups will be designated: group L (low HRV) and group N (normal HRV) based on the normal range for total power i.e.  $3466 \text{ ms}^2 \pm 1018 \text{ ms}^2$ .

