### Sample size

There is only one previous study that has looked at the autonomic dysfunction in patients with cervical myelopathy. They had a sample size of 30 patients and majority of patients had either moderate or severe myelopathy. Currently there is no data on the incidence of low HRV in patients with varying severities of cervical myelopathy. We plan to recruit around 100 patients with various degrees of cervical myelopathy for this study. Around 25 % of patients will be mild to moderate myelopathy and rest will be moderate to severe. Hence this sample size will provide us the useful information on the true incidence of autonomic dysfunction across different severities of myelopathy.

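### Student's pooled-variance t test is named for parametric data, although group sizes are uncontrolled and nothing in the plan supports equal variances; Welch's test is safer for unpaired comparisons

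*Combined protocol and SAP*

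**What the plan says.** The Analysis section of the combined protocol and SAP sends within-group non-parametric HRV data to the Wilcoxon matched pairs test and between-group non-parametric HRV data to the Mann–Whitney test. It then adds "Student t test will be used for parametric data". It does not say which variables count as parametric, whether the t test is paired or unpaired, what alpha applies, or what happens if variances differ.

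Three other places bear on the sizes of the compared groups:

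- Study design: "This is a single centre, prospective observational study".
- The heart rate variability definition: "Based on HRV values, two groups will be designated: group L (low HRV) and group N (normal HRV"), with membership decided by total power.
- Sample size: "We plan to recruit around 100 patients with various degrees of cervical myelopathy for this study". It also says "Currently there is no data on the incidence of low HRV in patients with varying severities of cervical myelopathy" and gives one split, by severity: "Around 25 % of patients will be mild to moderate myelopathy and rest will be moderate to severe".

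**The concern.** Student's unpaired test pools the two sample variances. When the true SDs differ, pooling gives the right standard error only if the groups are about equal in size. Here nothing holds the groups equal. L and N are sorted by a measurement, and the plan says the frequency of low HRV is unknown. Severity groups are expected to be unequal.

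At stake are the p-values and confidence intervals of whatever unpaired parametric comparisons are reported. If the smaller group is the more variable, p-values are too small and intervals too narrow. If the larger group is, the reverse holds. The sponsor cannot know the direction in advance.

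**Working it through.** The plan has no figure to reproduce, because it states no alpha, SD, effect size or power.

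**Inputs**

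- Test: Student's t (Analysis).
- Total N: 100 (Sample size, approximate).
- Alpha: not stated; assumed two-sided 5%.
- SD ratio between groups: not stated; assumed 1.5, with 1.25 and 2 as a range.
- Split: not stated for L:N; 50/50, 60/40 and 75/25 are tried as assumptions. The plan's own 25/75 figure is by severity.
- Data: normal.

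**Formulas** (group 1 is the smaller)

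- True variance of the mean difference: V = s1²/n1 + s2²/n2.
- Variance that Student's test uses, on average: E = sp²(1/n1 + 1/n2), with sp² = [(n1−1)s1² + (n2−1)s2²]/(n1+n2−2).
- Approximate rejection rate under the null: 2[1 − Φ(c√(E/V))], with c = t(0.975; 98 df) = 1.984.

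**75/25, smaller group more variable** (s1 = 1.5, s2 = 1)

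- V = 2.25/25 + 1/75 = 0.1033
- sp² = (24×2.25 + 74×1)/98 = 1.306; E = 1.306 × 0.05333 = 0.0697
- √(E/V) = 0.821; 1.984 × 0.821 = 1.629; rate ≈ 10.3%

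**75/25, larger group more variable** (s1 = 1, s2 = 1.5)

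- V = 1/25 + 2.25/75 = 0.0700
- sp² = (24×1 + 74×2.25)/98 = 1.944; E = 0.1037
- √(E/V) = 1.217; 1.984 × 1.217 = 2.415; rate ≈ 1.6%

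**50/50** (s1 = 1.5, s2 = 1)

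- V = 3.25/50 = 0.065; sp² = 1.625; E = 1.625 × 0.04 = 0.065
- E = V, so pooling does no harm.

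The approximation runs slightly low: it gives 4.7% where the true rate is 5%. Simulation removes that error:

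| Split | SD ratio | Student, smaller group more variable | Student, larger group more variable |
|---|---|---|---|
| 50/50 | 1.5 | 5.0% | 5.0% |
| 60/40 | 1.5 | 7.0% | 3.5% |
| 75/25 | 1.25 | 7.9% | 2.9% |
| 75/25 | 1.5 | 10.7% | 1.8% |
| 75/25 | 2 | 15.2% | 0.8% |
| any | 1 | 5.0% | 5.0% |

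Simulations of different lengths put the 10.7% entry between 10.3% and 10.8%. At the most extreme setting tried (90/10, ratio 2) the two rates were 24.8% and 0.1%. Welch's test stayed between about 4.8% and 5.2% in every setting.

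**Cost of Welch if variances are equal** (75/25, assumed true difference 0.6 SD): power 73.0% with Student and 71.8% with Welch, a loss of 73.0 − 71.8 = 1.2 points. At 50/50 there is no loss.

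**The case against.** The case against is that these inputs are not the plan's.

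- **Split.** A reader might take 25/75 as the expected L:N split. It is not: the Sample size section applies it to myelopathy severity. The nearest figure to an L:N split is in the Background, "autonomic nervous system involvement in up to 50% of patients with compressive cervical myelopathy". That concerns autonomic involvement rather than the total-power cut-off, and it allows an even split, at which the problem vanishes. The Hypothesis also expects decreased HRV to be common. If L were the more variable group and the majority, Student's test would be conservative.
- **Spread.** A reader might infer that the plan's own theory predicts unequal variances, because its rationale says "heart rate variability may be used as a predictor of haemodynamic fluctuations under anaesthesia". That passage is about instability within patients under anaesthesia. It says nothing about variance between patients in L versus N, and no group SD appears anywhere.
- **Scope.** The stated aims are incidences and a correlation, and hypotension is classified into categories. The t test is a residual line with no named variable. In paired use the equal-variance issue does not arise.

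All of this stands, and it limits the size of the point. It does not restore the case for pooling. The plan gives no more support for equal variances than for unequal ones, and the split will be known only after the data are in. Moving data to Mann–Whitney is no remedy for unequal spread either: at 75/25 with SD ratio 1.5, a simulation of 5,000 replicates gave about 7.8% and 3.2%.

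**Conclusion.** The point holds as a minor one. For unpaired parametric comparisons the plan names a test whose error rate depends on equal group sizes or equal variances, and it secures neither. At 75/25 with SD ratio 1.5, the rate is 10.7/5 = 2.1 times nominal in one direction and 1.8/5 = 0.36 of nominal in the other. Those figures rest on an assumed alpha, split and SD ratio and on normal data. With even groups or equal SDs there is no distortion.

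The documents do not support saying that this study's false-positive rate is doubled, or that its main findings are affected. The incidences of low HRV and hypotension do not use this test.

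**What to change.** In the Analysis section, replace the sentence on the t test with:

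> Unpaired comparisons of parametric data will use Welch's unequal-variance t test, reported as mean difference with 95% CI; within-group comparisons of parametric data will use the paired t test.

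Both halves are needed. The section includes within-group comparisons, so assigning Welch's test to all parametric data would put an independent-samples test on paired measurements.

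The change needs no extra patients or data and does not touch clinical care. Its price is the small power loss shown above if variances turn out equal. Naming the test now also avoids choosing between Student and Welch after seeing the variances.

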### *1. Heart rate variability*

The Task Force of the European Society of Cardiology and the North American Society of Pacing and Electrophysiology has standardized guidelines for the measurement of heart rate variability (14). These recordings will be analysed and power spectrum densities will be calculated for total power (TP) which is a measure of heart rate variability. Low frequencies (LF), high frequencies (HF) and LF: HF ratio will also be analysed. Based on HRV values, two groups will be designated: group L (low HRV) and group N (normal HRV) based on the normal range for total power i.e.  $3466 \text{ ms}^2 \pm 1018 \text{ ms}^2$ .

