### Trial Population

The study participants will be recruited from patients with cervical myelopathy presenting for cervical spine surgery at Toronto Western Hospital.

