### Inclusion Criteria

Adults patients, aged 18 – 70 years with the history of cervical myelopathy, presenting for anterior or posterior cervical decompression and fusion.

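### Low HRV is cut at 3466 ± 1018 ms² with ± undefined and no control group, so the proportion below the cut should not be read as the incidence of autonomic dysfunction, and the hypotension and severity analyses should not rest on the cut alone

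*Combined protocol and SAP*

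**What the plan says.** The Analysis section announces "The incidence of low HRV as indicated by a total power below the normal range of" 3466 ms² ± 1018 ms². Definition 1 (Heart rate variability) repeats the range and uses it to form "group L (low HRV) and group N (normal HRV) based on the normal range for total power". Neither place says what ± stands for, writes out the cut-off, or describes the reference sample. Reference 14 is cited in Definition 1 for how HRV is measured, not for this range.

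The same cut covers all participants, "aged 18 – 70 years with the history of cervical myelopathy". The design is one cohort: "This is a single centre, prospective observational study", with participants "recruited from patients with cervical myelopathy presenting for cervical spine surgery". No comparison group without myelopathy is described.

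The stated aim is to "determine the incidence of abnormalities in HRV in patients undergoing surgery for cervical myelopathy", and the Hypothesis section likewise speaks of decreased HRV. The Sample size section goes further and says that the study will inform on "the true incidence of autonomic dysfunction across different severities of myelopathy". The Analysis section also plans: "We will determine the correlation between low HRV, hypotension and the severity of myelopathy". That is stated for low HRV, so it uses the same binary variable.

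**The concern.** Any lower reference limit leaves some healthy people below it. How many depends on what ± 1018 is, and the plan does not say. With no control group, the study cannot estimate that background share itself. A count of patients below 2448 ms² then mixes those with autonomic dysfunction and those who are merely at the low end of normal, in unknown parts.

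Two things are at stake. The first is the reading of the main proportion, since the first hypothesis is that decreased HRV is common. The second is the relation of HRV to hypotension and to severity of myelopathy. As written, it passes through a cut-off of uncertain meaning and loses information by splitting a continuous measure in two.

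**Working it through.** **Inputs.** From the documents: range 3466 ± 1018 ms² (Analysis; Definition 1); about 100 patients (Sample size); autonomic involvement in up to 50% of patients in an earlier study (Background). Assumed, because the documents do not give them: the meaning of ±, and a normal or log-normal reference distribution with the same mean and SD.

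**1. Cut-off.** 3466 − 1018 = 2448 ms².

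**2. Share of reference-like people below 2448 ms².**
- ± is one SD, normal: Φ((2448 − 3466)/1018) = Φ(−1) = 15.9%. Log-normal: σ = √ln(1 + (1018/3466)²) = 0.288, median 3326 ms², share 14.3%.
- ± is 1.96 SD, so SD = 1018/1.96 = 519: normal Φ(−1.96) = 2.5%; log-normal 1.2%.

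**3. When the meaning of ± changes the conclusion.** Smallest count of 100 whose Wilson 95% lower limit exceeds the background share, treating that share as known:

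| Meaning of ± | Background (normal / log-normal) | Count needed (normal / log-normal) |
|---|---|---|
| one SD | 15.9% / 14.3% | 24 (CI 16.7–33.2%) / 22 (15.0–31.1%) |
| 1.96 SD | 2.5% / 1.2% | 6 (2.8–12.5%) / 4 (1.6–9.8%) |

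The two meanings disagree for about 4 to 23 low per 100. Example: 20 of 100 (CI 13.3–28.9%) is compatible with background under one SD and clearly above it under 1.96 SD. At 50 of 100 (CI 40.4–59.6%) both say raised.

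**4. If the reference sample differs from these patients.** Suppose that healthy peers have a mean 20% lower with the same coefficient of variation (an assumption): mean 2773, SD 814. Then Φ((2448 − 2773)/814) = Φ(−0.40) = 34.5% would be low with no dysfunction. A background share taken from ± alone could therefore make a normal cohort look abnormal.

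**5. Direction of bias.** With prevalence p, sensitivity Se and background share b, the proportion low is p·Se + (1 − p)·b. It equals p when Se = 1 − ((1 − p)/p)·b. At p = 50% and one SD this is 84% (normal) or 86% (log-normal). Above that the proportion overstates dysfunction; below it, it understates. The documents give no sensitivity, so the direction is unknown.

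**6. Cost of the L/N split.** If ln(total power) is normal and linearly related to the outcome, a split with fraction q in group L keeps φ(z_q)²/(q(1 − q)) of the information.
- q = 0.159: 0.242²/(0.1587 × 0.8413) = 44%, correlation multiplied by √0.44 = 0.662.
- q = 0.5: 0.399²/0.25 = 64%, correlation multiplied by 0.798.

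Smallest detectable correlation, n = 100, 80% power, two-sided 5%: tanh(2.802/√97) = 0.277 with the continuous measure. After the split, the underlying correlation must be 0.277/0.798 = 0.35 to 0.277/0.662 = 0.42.

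**7. Lower reference limit if ± is one SD.** 2.5th percentile: 3466 − 1.96 × 1018 = 1471 ms² (normal) or exp(ln 3326 − 1.96 × 0.288) ≈ 1892 ms² (log-normal).

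**The case against.** The rule can be applied as it stands: below the range means below 2448 ms², and everyone else falls in group N. The proportion below a fixed value is a valid description of the cohort. The aim, hypothesis and analysis all speak of HRV, and only one phrase in the sample-size rationale speaks of autonomic dysfunction. The meaning of ± may be clear in a source that we cannot see. Comparisons within the cohort need no healthy controls. The Analysis section also plans Mann–Whitney tests of HRV between groups; if those groups are the blood-pressure groups, part of the hypotension analysis is already free of the cut.

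Most of this stands, and it limits the point. A reader might infer that the meaning of ± settles the main conclusion whatever the result. It does not: outside about 4 to 23 per 100, the one-SD and 1.96-SD readings agree. A reader might also infer that the proportion overstates dysfunction, but the direction depends on a sensitivity that the documents do not give. Reading ± as a standard error would give a larger background share still, but it fits poorly with text that twice calls this a normal range. Nor should the proportion be tested formally against a background share derived from ±, for the reason in step 4.

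What the objection does not answer is the phrase in the Sample size section, or the correlation stated for low HRV. The Mann–Whitney groups are not named and no age adjustment is planned, so a cut-off-free analysis is not clearly in the plan.

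**Conclusion.** The point holds in a limited form. The low-HRV proportion describes the cohort, but it is not the incidence of autonomic dysfunction: the background share is about 14–16% if ± is one SD and about 1–2.5% if it is 1.96 SD, and there is no control group to settle it. Results above about 23 per 100 exceed background under both readings, provided that the reference sample resembles these patients in age and recording conditions, which the study cannot check. The L/N split keeps about 44–64% of the information in total power, under assumed normality and linearity. All these figures rest on assumed meanings of ± and assumed distributions. This is a cheap improvement to the reporting and analysis, not a fault that invalidates the study.

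**What to change.** 1. **Sample size section.** Replace the phrase on the true incidence of autonomic dysfunction with *proportion with total power below 2448 ms²*, reported with a 95% CI. Establish from the source of the range what ± 1018 is and who was measured, and cite it. Give the background share that follows as context only, not as a test, because the age and conditions of the reference sample may differ.
2. **Analysis section.** Alongside the L/N split, analyse ln(total power) as a continuous variable against hypotension and against mJOA, with age as a covariate. These results then do not depend on the cut-off.
3. **Sensitivity analysis.** If the source shows that ± is one SD, repeat the proportion at a lower reference limit, stating the assumed shape: 2.5th percentile about 1471 ms² (normal) or 1892 ms² (log-normal).

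Cost: a few sentences and a little more analysis. No new data are needed, since the ECG recordings are kept for later analysis (Study protocol) and demographics and the myelopathy score are collected (Data Collection). The downside is a more modest reading of the proportion, and a smaller low group in the sensitivity analysis.

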### *2. Blood Pressure*

Hypotension will be defined as a mean arterial blood pressure less than 70 mmHg lasting more than 1 min as measured using arterial line. Non-invasive measurement will be taken if arterial line is not available. Based on the blood pressure, patients will be classified into 3 groups

Group 1: no episodes of hypotension i.e. mean blood pressures at or above 70 mmHg

Group 2: hypotension i.e. means blood pressures below 70 mmHg with minimal intervention (<5 interventions)

Group 3: severe hypotension i.e. means blood pressures below 60 mmHg or MAP<70 mmHg needing multiple interventions or infusions of ionotropes.

All interventions for the treatment of hypotension will be recorded. The interventions include phenylephrine 40 mcg, Ephedrine 5 mg, fluid bolus and decrease the anesthetic level (inhalational or intravenous). Infusion of vasopressors and also total vasopressor dose will be recorded separately.

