Anesthetic induction may cause hypotension and this may be profound in some patients. Common causes of post-induction hypotension include vasodilatation, myocardial depression (6), hypovolemia and altered autonomic nervous system activity. Studies have shown that

patients with autonomic system dysfunction are more prone to anaesthesia induced hypotension. It has been shown that patients with autonomic dysfunction require increased vasopressor support to maintain blood pressure (7). Hence patients with cervical myelopathy, because of their associated autonomic system dysfunction, are possibly more prone to hypotension on induction of anaesthesia. This hypotension may put these patients at risk for spinal cord ischemia. Identifying patients at risk for hypotension can be useful to prevent hypotension and to prepare to treat hypotension sooner so that the risk of spinal cord ischemia can be minimized.

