## 2. Study protocol

Before general anesthesia, following a 10 minute stabilization period with the patient lying supine and breathing at a rate of 12 – 15 breaths per minute, a 5 minute ECG recording will be obtained. ECG data will be downloaded onto a study laptop for later analysis using LabChart Software (ADInstruments, Colorado Springs, CO, USA) to determine HRV values (Total power, high frequency, low frequency and low frequency : high frequency ratios). Hemodynamic data (heart rate, systolic diastolic and mean blood pressure) and depth of anaesthesia (Entropy) will be collected from the preinduction period until skin incision at 1 minute intervals. The study will be complete after skin incision.

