## Data Collection and Management

### Data Collection

The following data will be collected: patient demographics, surgical data including position technique, number of levels, duration, anaesthetic data including agents used, hemodynamic measurements from preinduction to surgical incision, Japanese Orthopaedic Association Score. The incidence of hypotension and the number of interventions required to keep mean arterial blood pressure above 70 mmHg will be recorded.

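### Hypotension is defined by fixed MAP cuts and no use of the collected preinduction MAP is stated, so a difference in starting pressure between HRV groups could mask or create an association

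*Combined protocol and SAP*

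**What the plan says.** All references are to the combined protocol and SAP.

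- **Event (Blood Pressure item under Definitions):** "Hypotension will be defined as a mean arterial blood pressure less than 70 mmHg lasting more than 1 min as measured using arterial line".
- **Groups (same section):** "Group 1: no episodes of hypotension i.e. mean blood pressures at or above 70 mmHg"; Group 2 is "hypotension i.e. means blood pressures below 70 mmHg with minimal intervention (<5 interventions"; Group 3 is "severe hypotension i.e. means blood pressures below 60 mmHg or MAP<70 mmHg needing multiple interventions or infusions of ionotropes". None of these refers to the patient's own starting pressure.
- **Data available:** under 2. Study protocol, haemodynamic data including mean pressure "will be collected from the preinduction period until skin incision at 1 minute intervals". The Data Collection section likewise lists "hemodynamic measurements from preinduction to surgical incision".
- **Analysis:** the section names the incidence of low HRV and of hypotension, and an unspecified correlation between low HRV, hypotension and myelopathy severity. It assigns Wilcoxon and Mann-Whitney tests to HRV data and a t test to parametric data without naming variables. Preinduction MAP has no stated role as an endpoint component, a covariate or a descriptive variable.
- **Rationale (Background):** because of autonomic dysfunction these patients "are possibly more prone to hypotension on induction of anaesthesia". The Background and the standard management section both tie the 70 mmHg level to intraoperative pressure.

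**The concern.** Crossing a fixed level combines two things: the pressure the patient starts from and the size of the fall. The autonomic rationale concerns the second.

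Starting pressure is likely to vary here. Ages run from 18 to 70, and none of the five exclusions concerns hypertension or baseline pressure. Groups L and N are formed from each patient's measured total power, so nothing in the design balances starting MAP between them.

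Two consequences follow if HRV and starting MAP are related:

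- If low-HRV patients start higher, a truly larger fall in them can be cancelled by their greater distance from 70 mmHg. If they start lower, an association can appear with no difference in response.
- An HRV association found without the baseline in the model leaves open whether HRV predicts hypotension any better than the pressure already on the monitor before induction.

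**Working it through.** **No planned figure to reproduce.** The Sample size section gives around 100 patients with no event rate, effect size, alpha or power. It gives no MAP distribution either. Apart from the 70 mmHg cut and the 100 patients, every input below is an assumption.

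**Step 1: fall needed to reach 70 mmHg.** Required fall = 1 − 70/start.

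| Starting MAP (mmHg) | Fall needed | MAP after a 30% fall |
|---|---|---|
| 80 | 12.5% | 56 |
| 90 | 22.2% | 63 |
| 100 | 30.0% | 70 |
| 110 | 36.4% | 77 |

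The same 30% fall is below the cut from 90 mmHg and in Group 1 from 110 mmHg.

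**Step 2: how much of the lowest MAP comes from the start.** With lowest MAP = start − fall, the two independent, and SDs of 12 and 10 mmHg, the share from the start is 144/(144 + 100) = 59%. If the fall instead scales with the start (mean 28%), keeping 10 mmHg for the spread due to the fall, the share is (0.72 × 12)²/[(0.72 × 12)² + 100] = 43%. A grid of 54 proportional-fall scenarios (mean start 90, 98 or 105 mmHg with SD 8, 12 or 15; mean fall 25% or 30% with SD 8, 10 or 15 points) gave 11% to 70%. The start clearly outweighed the fall in about 16 of the 54.

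**Step 3: effect on the group comparison.** Additive model: SD of lowest MAP = √244 = 15.6 mmHg, and P(below 70) = Φ[(70 − (start − fall))/15.6]. Mean falls are 28 mmHg (low HRV) and 22 mmHg (normal HRV); the normal group starts at 95 mmHg.

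| Low-HRV start (mmHg) | Low HRV below 70 | Normal HRV below 70 |
|---|---|---|
| 95 | 58% | 42% |
| 98 | 50% | 42% |
| 101 | 42% | 42% |
| 103 | 37% | 42% |

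Now let the mean fall be 25 mmHg in both groups, so HRV has no effect. A start of 95 gives Φ(0) = 50%, and a start of 103 gives Φ(−8/15.6) = 30%. The 20-point difference is due to starting pressure alone.

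**Step 4: rejection rates at 100 patients, two-sided 0.05, baseline difference 8 mmHg.** The unadjusted comparison is set against logistic regression adjusted for preinduction MAP.

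| Scenario | Model | Unadjusted | Adjusted |
|---|---|---|---|
| No HRV effect on the fall | additive, as step 3 | about 50% | 4% |
| No HRV effect on the fall | proportional, range of spreads | 23–68% | 4–5% |
| True HRV effect on the fall | additive, as step 3 | 8% | 43% |
| True HRV effect on the fall (6 points) | proportional, range of spreads | 4–6% | 25–67% |

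The proportional runs assume half the patients have low HRV, mean start 98 mmHg and mean fall 28%. With balanced baselines and the 6-point effect, power in those runs is 26–67% unadjusted and 29–75% adjusted, so adjustment costs nothing when it turns out not to be needed.

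The simulations ignore treatment and the one-minute duration rule, and take the fall (in mmHg or as a percentage) as independent of the start.

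**The case against.** The strongest reply is that the endpoint does what the plan asks. The stated aim and hypothesis are that low HRV predicts hypotension, and the Significance section is about finding patients at risk so that cord ischaemia can be limited. For that purpose a patient who falls from 76 to 69 mmHg is a case, and one who falls from 110 to 72 is not. This stands. A reader might infer that the 70 mmHg endpoint is wrong because HRV is meant to predict the size of the fall; the documents do not support that.

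A reader might also infer that the endpoint mostly measures where each patient started. That rests on one assumed pair of SDs. The range in step 2 supports partly, not largely. Nor is 70 mmHg the sole criterion: Group 3 adds 60 mmHg and treatment burden, though neither is relative to baseline. And the preinduction MAP is not ruled out of use: no use is stated, and the t test names no variables.

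The harm is also conditional. No passage links HRV to starting MAP, and with equal starts the endpoint shows the assumed effect in the right direction (58% against 42%).

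Finally, replacing the endpoint by the fall in MAP up to the first vasopressor dose would not cure the problem. Treatment aimed at 70 mmHg cuts the fall off near start − 70. Under the step 3 assumptions, with treatment on crossing 70, a true 6 mmHg difference shrinks to 3.0. With no true difference and starts 8 mmHg apart, a spurious 3.1 mmHg appears, which vanishes on adjustment for preinduction MAP.

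What survives is narrower: an observational comparison with no stated adjustment for a variable that enters the outcome directly and is already collected.

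**Conclusion.** The point holds as a missing analysis, not as a faulty endpoint. The event is defined entirely on absolute MAP and treatment criteria, preinduction MAP is available every minute, and the plan states no use for it. Any relation between HRV and starting MAP can therefore mask or create an association, and the plan could not show prediction beyond starting pressure.

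The size cannot be fixed from the documents. Under the assumptions shown, a 6 mmHg higher start in the low-HRV group cancels a 16-point difference in risk (58% against 42%), and 8 mmHg reverses it. An 8 mmHg difference with no HRV effect raises the false-positive rate from a nominal 5% to between 23% and 68%. If HRV and starting MAP are unrelated, there is no bias. The trial's own data will show which case applies, but only if the analysis is planned.

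**What to change.** In the Analysis section:

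1. Keep the unadjusted comparison on MAP below 70 mmHg as it stands.
2. Add a prespecified logistic regression of hypotension on HRV with preinduction MAP as a continuous covariate, and report it beside the unadjusted result. Define preinduction MAP as the mean of the supine readings before induction, and state the time window.
3. Tabulate preinduction MAP by HRV group, so that readers can see whether the two results should differ.
4. Optionally, as a supporting secondary analysis, report the largest fall in MAP from the preinduction value up to the first recorded intervention of any kind (vasopressor, fluid bolus or reduced anaesthetic level). Adjust it too for preinduction MAP, and state that treatment near 70 mmHg truncates the fall.

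The unadjusted result should remain because starting pressure may itself reflect autonomic state; in that case adjustment removes part of what HRV carries. Odds ratios also change on adjustment even without confounding, so the two should not be compared as if any shift were bias.

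The cost is a few sentences, one extra model term and, if step 4 is taken up, one more secondary analysis. No new measurement is needed and patient management is unaffected.
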